APPENDIX 2 – PHARMACOKINETICS BLOOD SAMPLING

The procedures described in this appendix detail the requirements for blood sampling and handling for pharmacokinetics samples.

Collection, processing, and transport will all be conducted with the samples shielded from light to minimize photo-degradation of any potential light-sensitive bismuth metabolite(s) within the samples.

1) Quantity collected and timeframe:

The total volume of blood drawn for bismuth and trimethylbismuth (TMB) pharmacokinetic assessment is anticipated to be 56 mL (8 x 7 mL tubes) over the full study period for each subject.

Blood samples will be drawn at two (2) timepoints in the study – one blood draw (amounting to 4 tubes, 7 ml each) will be done prior to the start of treatment with Pylera® plus PPI (presumed to be omeprazole) (Inclusion Visit), and a second blood draw sample (amounting to 4 tubes, 7 ml each) the day after the end of treatment with Pylera® plus PPI (EOT Visit). The date and time of the two blood samplings will be recorded and reported for each subject. The collection tubes will be shielded from light to minimize photo-degradation and frozen at -20°C before transport for measurement of bismuth and TMB concentration.

2) Type of tubes

Blood samples will be obtained from an antecubital vein using two types of tubes:

- For bismuth plasma concentration determination: coded EDTA K2 Vacutainers tubes or equivalent (1 x 7 mL tube),
- For bismuth whole blood concentration determination: coded sodium citrate-coated Vacutainer tubes or equivalent (1 x 7 mL tube).
- For TMB whole-blood concentration determination: coded sodium citrate-coated Vacutainer tubes or equivalent (2 x 7 mL tubes).

3) Processing

Processing of one (1) blood sample per patient for bismuth plasma concentration determination:

Following collection, each 7 mL EDTA tube will be centrifuged at 4°C and 1500 g for 10 minutes; the resulting plasma will be extracted and divided into even numbers of opaque polypropylene snap-cap tubes (minimum two tubes) and frozen at a minimum of -20°C until shipment to the central laboratory for analysis of bismuth plasma concentrations.

Processing of one (1) blood sample per patient for bismuth whole blood concentration determination:

The 1 x 7 mL sample will be drawn on citrate-coated tubes not centrifuged, protected from light and frozen at -20°C before transport for whole blood measurement of bismuth.

Processing of two (2) blood samples per patient for TMB whole-blood concentration determination:

The 2 x 7 mL samples will be drawn on citrate-coated tubes not centrifuged, protected from light and frozen at -20°C before transport for whole-blood measurement of TMB.

4) Transport and concentration determination

All sample tubes will be labeled with the study identification number, subject identifier, and time of sampling. Samples will be stored in an opaque box and frozen at a minimum of -20°C until shipment to the central laboratory. Transfer to the central laboratory will be done by an approved transporter under frozen conditions and with samples being shielded from exposure to light.

The central laboratory will receive and store all shipped samples and will distribute plasma and whole blood samples to the analytical facilities for analysis of total bismuth. The TMB metabolite concentration determination will be determined once bismuth concentration is known.

5) Additional third blood sample

This sampling and processing procedure will also be used only if a subject is requested to return to provide a third confirmatory plasma and whole blood sample for bismuth analysis in case of clinical symptoms indicative of bismuth-related neurological adverse events or bismuth accumulation at the EOT Visit (total bismuth in whole blood > 50 µg/L).

APPENDIX 3 – CENTRAL NERVOUS SYSTEM ADVERSE EVENTS OF INTEREST

Bismuth neurotoxicity is typically characterized by encephalopathy, which is defined as any degenerative or diffuse disease of the brain that alters brain structure or function.

In order to select the appropriate terms, the original Standardized MedDRA Query (MedDRA 15.1SMQ Noninfectious encephalopathy/delirium (20000133)) was revised to specifically address the bismuth encephalopathy and include signs and symptoms that are specific to this risk.

Preferred Terms (narrow scope): Encephalopathy, Toxic encephalopathy

Preferred Terms (broad scope):

Abnormal behavior;	apraxia; Gait disturbance;	changes; Mood altered;
Agitation; Agraphia; Alexia;	Generalised non-convulsive	Myoclonus; Paresis anal
Altered state of	epilepsy; Grand mal	sphincter; Partial seizures;
consciousness; Amnesia;	convulsion; Hallucination;	Partial seizures with
Anal sphincter atony;	Hallucination, auditory;	secondary generalization;
Apathy; Ataxia; Bladder	Hallucination, gustatory;	Personality change;
sphincter atony; Cerebellar	Hallucination, olfactory;	Personality disorder;
ataxia; Cerebellar syndrome;	Hallucination, synaesthetic;	Psychomotor seizures;
Clonic convulsion; Coma;	Hallucination, tactile;	Restlessness; Simple partial
Coma scale abnormal;	Hallucination, visual;	seizures; Sleep disorder;
Complex partial seizures;	Hallucinations, mixed;	Slow response to stimuli;
Confusional state;	Hypersomnia;	Sluggishness; Somnolence;
Convulsion; Convulsions	Hyporesponsive to stimuli;	Speech disorder; Stupor;
local; Coordination abnormal;	Illogical thinking	Thinking abnormal; Tonic
Delirium; Depressed level of	Incontinence ; Judgement	convulsion; Tremor;
consciousness; Disturbance in	impaired; Lethargy; Listless;	Unresponsive to stimuli;
attention; Dysarthria;	Loss of consciousness;	Urinary incontinence.
Dysgraphia; Dyspraxia;	Memory impairment; Mental	
Faecal incontinence; Gait	impairment; Mental status	

A “narrow” scope represents the condition of interest and a “broad” scope helps to identify all possible cases, including some that may prove to be of little or no interest on closer inspection. Thus, a “narrow” search yields “specificity” while the “broad” search yields “sensitivity.”

The presence of these events will be identified and assessed at the End of Treatment and End of Study visits only as the event would need to be treatment-emergent in order to be potentially associated with potential bismuth neurotoxicity.

Of note is the follow-up for serious adverse events (SAEs) of encephalopathy, which will be ensured through a separate intensive monitoring program comprising a “neurological disorders and bismuth” questionnaire (specific to the Intensive Monitoring Program and not part of this study) to be completed for each case, followed by case review and confirmation by the Scientific Committee of the Intensive Monitoring Program.

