9.1.2 Observations and Measurements

Following the granting of Informed Consent, each subject will be assigned a subject number in sequential order.

The following Inclusion Visit procedures and evaluations in addition to procedures normally conducted as part of standard of care will be performed after Informed Consent will be recorded in the appropriate sections of the CRF:

- Demographic data
- Confirmation of inclusion and exclusion criteria
- Date of Pylera® prescription
- Name of prescribed PPI
- Vital signs measurement (blood pressure, pulse rate), height and weight
- Disease history regarding *H. pylori* infection with previous *H. pylori* treatment and diagnostic tests with date and results (negative/positive)
- Co-morbidities, medical/surgical history
- Recording of prior and concomitant medications

Subjects will provide one blood sample as the baseline sample (D0 sample) for assessment of plasma and whole blood bismuth concentrations and whole blood trimethylbismuth (TMB) concentrations as per the procedures outlined in Appendix 2.

Once the D0 sampling is complete, subjects will be given an appointment for the second blood sampling (D11 sample) and subjects may initiate treatment with Pylera®.

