9.2.1 Subjects who completed treatment with Pylera®

Subjects who have completed the 10-day treatment with Pylera® will return to complete the following procedures as part of the EOT Visit:

- Vital signs measurement (blood pressure, pulse rate)
- Recording Pylera® treatment description and compliance
- Recording of concomitant medications
- Recording of AEs

The presence of CNS adverse events of specific interest as listed in Appendix 3 will be assessed at this visit with the specific form “Pharmacovigilance reporting form-neurological disorders and bismuth” developed for the collection of the adverse events of special interest as part of the Intensive Monitoring Program that will be completed by the Investigator.

Subjects will provide one blood sample as the post-treatment sample (D11 sample) for assessment of plasma and whole blood bismuth concentrations as well as whole blood TMB concentrations as per the procedures outlined in Appendix 2.

Subjects who demonstrate bismuth accumulation in whole blood at the EOT Visit ($> 50 \mu\text{g/L}$) will be requested to return immediately to the laboratory to draw a third blood sample for evaluation of bismuth. If bismuth concentration remains sustained and subject interview with Investigator confirms that no third-party source of bismuth was consumed outside of the context

of this study, the subject will be referred to the separate Intensive Monitoring Program to be evaluated for inclusion.

Subjects will return 28 days after the EOT Visit to complete the EOS Visit. At this visit, subjects will complete:

- Vital signs measurement (blood pressure, pulse rate)
- Recording eradication test
- Recording of concomitant medications
- Recording of AEs

The presence of CNS adverse events of specific interest as listed in Appendix 3 will be assessed at this visit with the specific form “Pharmacovigilance reporting form-neurological disorders and bismuth” developed for the collection of the adverse events of special interest as part of the Intensive Monitoring Program that will be completed by the Investigator.

Subjects who demonstrate a positive diagnostic *H. pylori* test (breath test, biopsy, or other test at the discretion of the Investigator) at End of Study will be documented by the completion of a specific form entitled “Targeted follow-up form – Pylera® eradication therapy failure”. These subjects will be referred to treatment for *H. pylori* infection outside of the context of this study.

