10.2 PRE-EXISTING MEDICAL CONDITIONS

Any pre-existing medical conditions, which do not worsen in duration, intensity or frequency during the study are not considered to be AEs. These pre-existing medical conditions should be adequately documented in the medical history of the CRF and any other appropriate ancillary documents. Pre-existing medical conditions, which worsen after exposure to study treatment will be recorded as an AE on the Adverse Event Form of the CRF.

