10.4.1 Assessment and Recording

An AE, whether or not considered causally related to the treatment, must be promptly documented and recorded. At each study visit, after the subject has had an opportunity to spontaneously mention any problems, the Investigator should inquire about AEs by asking the appropriate open questions. In addition to straightforward subject observation (e.g., headache, nausea, etc.), AEs will also be documented from any data collected in the CRF (e.g., laboratory values, physical examination findings, etc.) or other documents (e.g., subject diaries) that are relevant to subject safety.

At each follow-up visit or assessment by phone or otherwise, all AEs, whether observed by the Investigator or one of his or her professional collaborators, or reported by the subject

spontaneously or in response to an open question, will be recorded in the Adverse Event Form included in the CRF with the following information.

- **Name of the AE:** Name should be a medical term. When possible, the Investigator should differentiate an illness entity from isolated symptoms or signs. For instance, the term “flu” should be recorded instead of listing all the flu-related symptoms. Where a differentiation is not possible, symptoms and signs should be separately recorded and evaluated as **Adverse Events**.
- **Start date and stop date (or statement that the event is continuing) of the AE**
- **Imputability of Pylera®:** evaluate the causal relationship between Pylera® and the AE as described in section 10.4.2
- **Seriousness criteria** as defined in section 10.1

The Aptalis Pharma US, Inc CRA who visits the center will check the completeness and accuracy of the Adverse Events Form. Wherever possible, all AEs regardless of the seriousness must be followed through resolution.

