11.7.7 Pharmacokinetic / Pharmacodynamic Analysis

This study will focus on the detection and assessment of bismuth concentrations within the circulating plasma and whole blood compartment.

The initiation of any encephalopathy by an external compound requires the absorption of the material(s) and its transport to the central nervous system and its eventual crossing of the blood-brain-barrier; material which is not absorbed and eventually excreted in the feces will have no potential to induce an encephalopathy.

It is not known which metabolite(s) (if any) bismuth subcitrate potassium transforms to following ingestion of Pylera® by patients, and how such metabolites are further transformed. In the context of the clinical cases reported in the 1970s, it was never confirmed which bismuth metabolites generated the bismuth-associated encephalopathies.

One metabolite – trimethylbismuth (TMB) – is produced by methanoarchaea bacteria^{31,32,33} present within the intestinal flora and is detectable at picogram levels within the circulating plasma compartment and by examination of respiratory exhalation³⁴. TMB has been implicated in

bismuth-associated encephalopathies following the demonstration of encephalopathies in experimental animals exposed by inhalation to large uncontrolled quantities of TMB³⁵.

The detection of total bismuth (metal) rather than individual bismuth metabolites permits the detection of all bismuth circulating within the bloodstream irrespective of whatever metabolite form the bismuth atom is found in. Whole blood TMB will be evaluated using an analytical method derived from Boertz *et al.* (2009)³⁴ due to the possibility of encephalopathy arising from animal models. Post-treatment plasma and whole blood concentrations of bismuth (metal and TMB) will be described after subtraction of the baseline value for each subject using the following formula:

$$\text{Accumulation Value} = (\text{EOT bismuth concentration} - \text{Day 0 bismuth concentration})$$

This comparison will include an evaluation of bismuth concentration in subjects who report neurological AEs and subjects who do not report neurological AEs.

After comparison on the whole sample, data will be stratified by the PPI used in combination with Pylera® and the comparison will be repeated in strata where sample size allows.

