16 APPENDICES

APPENDIX 1 – STUDY FLOWCHART

APPENDIX 2 – PHARMACOKINETICS BLOOD SAMPLING

APPENDIX 3 – CENTRAL NERVOUS SYSTEM ADVERSE EVENTS OF INTEREST

APPENDIX 1 - STUDY FLOWCHART

	Inclusion Visit (Day 0)	End of Visit (Day 11)	End of Study Visit (Day 39)
Informed Consent	X		
Demographics	X		
Inclusion/Exclusion criteria	X		
Vital Signs	X	X	X
Diagnostic tests done before Pylera® prescription ¹	X		
Co-morbidities, medical, surgical history	X		
Concomitant medications	X	X	X
Diagnostic H. pylori test (breath test, biopsy, or other test)	X		X ²
Pharmacokinetics sample	X	X ³	
Adverse events		X	X
CNS adverse events ⁴		X	X

1. Including information pertaining to prior *H. pylori* treatment.
2. At the discretion of the Investigator
3. Subjects who demonstrate bismuth accumulation at the End of Treatment Visit (> 50 µg/L) will be referred to the separate Intensive Monitoring Program to be evaluated for inclusion. In case of inclusion, patients will be requested to return to the laboratory to draw a third blood sample for evaluation of bismuth). In case of neurological AE indicative of bismuth encephalopathy (please refer to Appendix 3 – Central Nervous System Adverse Events of Interest) if present at Day 11 blood samples will be as quickly processed as possible.
4. For CNS adverse event indicative of encephalopathy, follow-up will be perform by Intensive Monitoring Program

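### CNS events of interest have no matched pre-treatment assessment, so whether they are new rests on general history and recalled onset dates

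*Protocol*

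**What the plan says.** Protocol Appendix 3 lists MedDRA terms in a narrow and a broad scope and states that these events are "identified and assessed at the End of Treatment and End of Study visits only as the event would need to be treatment-emergent". The flowchart in Appendix 1 agrees: its row for CNS adverse events is ticked at Day 11 and Day 39 and is blank at Day 0.

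For the EOT visit, and again for the EOS visit, section 9.2.1 says: "The presence of CNS adverse events of specific interest as listed in Appendix 3 will be assessed at this visit with the specific form". The Investigator completes that form.

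At inclusion, section 9.1.2 asks for "Co-morbidities, medical/surgical history", with prior and concomitant medications. It includes no CNS form and no targeted neurological question.

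Section 10.2 deals with conditions that were already there: "Any pre-existing medical conditions, which do not worsen in duration, intensity or frequency during the study are not considered to be AEs". It adds that "These pre-existing medical conditions should be adequately documented in the medical history of the CRF". Section 10.4.1 requires for each AE the "Start date and stop date (or statement that the event is continuing) of the AE".

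Section 11.7.7 then uses the neurological AEs to form groups: "This comparison will include an evaluation of bismuth concentration in subjects who report neurological AEs and subjects who do not report neurological AEs".

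**The concern.** The requirement that an event be treatment-emergent is an argument for a baseline assessment, yet Appendix 3 gives it as the reason for omitting one. Emergence is a change from pre-treatment status, and a change cannot be read from post-treatment visits alone.

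The broad list makes this matter. Beside seizures and coma it contains complaints that a patient may have had for some time without mentioning them: sleep disorder, somnolence, restlessness, lethargy, altered mood, memory impairment, tremor, urinary incontinence. Appendix 3 itself accepts that some broad-scope cases will turn out to be of little interest. A symptom nobody asked about on Day 0 can surface on Day 11, when attention is directed at this list.

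At stake is the make-up of the neurological AE group in section 11.7.7. Pre-existing symptoms in that group would tend to pull its bismuth level towards that of the other subjects and so hide a difference, if there is one. Status that is not recorded before the first dose cannot be recovered at analysis, so a later analysis plan cannot repair this.

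**Working it through.** **Comparison of the texts.** The protocol gives no figure on this point, so the main check is to set its provisions side by side.

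| Item | Day 0 | Day 11 and Day 39 |
|---|---|---|
| Appendix 3 CNS events (9.2.1, Appendix 1) | not assessed | assessed with a specific form |
| General history (9.1.2) | recorded | – |
| Bismuth (11.7.7) | measured | measured at Day 11; analysed as EOT minus Day 0 |
| Vital signs (11.7.6) | measured | measured; change from baseline summarised |

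Bismuth and vital signs are set against a baseline; CNS symptoms are not.

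The rule in section 10.2 turns on worsening in duration, intensity or frequency. Day 0 does not specifically record any of the three for Appendix 3 symptoms. The AE items in section 10.4.1 are name, start and stop date, causal relation to Pylera and seriousness; intensity and frequency are not among them. In practice the rule therefore rests on whatever entered the general history and on the onset date that the subject recalls.

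**Scale, for illustration only.** The one documentary input is N = 200 (section 4.1). Assumed inputs:
- t = proportion with a truly new event
- p = prevalence of pre-existing Appendix 3 symptoms
- m = share of those wrongly recorded as new

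False cases = N × (1 − t) × p × m.

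Share of the true group difference retained = t / [t + (1 − t) × p × m]. This assumes that bismuth in false cases is like that in non-cases.

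With t = 2%, that is 200 × 0.02 = 4 true cases:

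| p | m | False cases | Difference retained |
|---|---|---|---|
| any | 0% | 0 | 100% |
| 5% | 25% | 200 × 0.98 × 0.05 × 0.25 ≈ 2.5 | 0.02/0.03225 = 62% |
| 5% | 50% | 200 × 0.98 × 0.05 × 0.50 = 4.9 | 0.02/0.0445 = 45% |
| 10% | 50% | 200 × 0.98 × 0.10 × 0.50 = 9.8 | 0.02/0.069 = 29% |
| 20% | 100% | 200 × 0.98 × 0.20 × 1.00 ≈ 39 | 0.02/0.216 = 9% |

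Over t = 1% to 5%, p = 2% to 20% and m = 0% to 100%, the retained share runs from 100% down to about 5% (0.01/0.208, at t = 1%, p = 20%, m = 100%). The deciding quantity is m: how well general history and recalled dates stand in for a baseline assessment. The documents give no value for it.

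**The case against.** A reader might infer that pre-existing symptoms will be counted as treatment-emergent. The protocol does not support that. Section 10.2 excludes unchanged conditions, history is taken at Day 0, section 4.3.1 collects medication from the previous three months, and section 7 records the date of the first dose, against which an AE start date can be set. An Investigator can also ask about onset. These are real safeguards. What they leave open is the mild, untreated symptom that was never mentioned at inclusion.

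It is also tempting to treat the specific form as a symptom-by-symptom checklist. The form is not shown. Sections 10.4.3.3 and 11.7.6 describe a reporting form completed for each case with listed symptoms, and the end of Appendix 3 calls the bismuth questionnaire part of the separate monitoring programme and not of this study. How far elicitation differs before and after treatment is therefore uncertain. That the named events are assessed with a form at two visits and not at the first is clear.

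Three further inferences go too far:
- The study was not requested for CNS events. Section 1.2 says the request concerned bismuth concentrations; encephalopathy is the background worry.
- Avoidable third samples and referrals are not shown. Section 3.2 ties these to symptoms indicative of bismuth-related neurological events, which is a clinical judgement and not the presence of any broad-scope term.
- Section 11.7.7 does not define its neurological AE group as the Appendix 3 broad list, so the overlap is likely but not stated.

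The flowchart note that "For CNS adverse event indicative of encephalopathy, follow-up will be perform by Intensive Monitoring Program", with committee review of cases, does not close the gap. That review serves to confirm encephalopathy; nothing says it removes pre-existing symptoms from the study's own comparison.

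**Conclusion.** The point holds as a limited design weakness. The reason Appendix 3 gives for assessing CNS events only after treatment is a non sequitur, and emergence of mild broad-scope symptoms rests on general history and recalled onset. Misclassification is possible, not certain. It could blur the section 11.7.7 comparison of bismuth by neurological AE status.

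Its size cannot be derived from the documents. It is nil if section 10.2 works fully, and substantial only under assumed prevalences and error rates. The comparison is descriptive (section 11.7) and has no power calculation behind it (section 11.1). The primary result, bismuth accumulation, does not depend on it. The case for acting is that the remedy is cheap and that the missing baseline cannot be supplied later.

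**What to change.** - At the Inclusion Visit, before the first dose, record which Appendix 3 symptoms are present, as baseline status. Noting duration, intensity and frequency for any that are present would give section 10.2 the data it relies on.
- Add this to the Day 0 column of the Appendix 1 flowchart and to the list in section 9.1.2.
- Replace the Appendix 3 sentence that limits assessment to the two post-treatment visits.
- In section 11.7.7, count as neurological AEs for the bismuth comparison only symptoms that are new or worse than at Day 0, and say whether the group is defined by the Appendix 3 list.
- Reconcile section 9.2.1, which has the Investigator use the form at both visits, with the end of Appendix 3, which places the questionnaire outside this study.

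The referral and third-sample rules are left unchanged. The cost is a few minutes of extra paperwork at an existing visit and the text edits above, with no extra visit or blood sample.
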